2.2.2 Secondary objectives

- To determine if the *ablation-by-LAW* approach permits to be more efficient in terms of procedure time, RF time, and fluoroscopy time.
- To evaluate the rate of complications using the *ablation-by-LAW* approach.
- To analyze the reasons for not obtaining a first-pass isolation using the *ablation-by-LAW* approach.

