3. METHODS

3.1 Study design

Single-arm, international, multicenter, prospective study.

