3.5.2 Secondary endpoints

3.5.2.1 Acute procedural outcomes

- Procedure time (skin to skin)
- Radiofrequency time
- Number of applications (total/per RF line/per segment)
- Fluoroscopy time
- First-pass isolation rate
- Early PV reconnections

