3.11 Statistical analysis

3.11.1 Sample size

The sample size calculation has been based on the assumption that the proposed ablation protocol ('LAWT') is an acceptable alternative to the CLOSE protocol¹⁵ (non-inferiority), with the advantage of less radiofrequency applied and likely lower risk for complications. A non-inferiority margin of 10% of clinical success (arrhythmia-free survival one year after the ablation procedure) will be considered to be the largest difference that is acceptable

between both protocols for LAWT to be adopted in clinical practice. Recruiting $n = 106$ participants will be required to confer 90% power to reject the inferiority null hypothesis, that is, that the lower limit of a one-sided 95% confidence interval will be above the non-inferiority limit of -0.05 , indicating no difference between the arms. A drop-out rate of 10% is estimated, and included in the sample size calculation.

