3.11.2 Statistical methods

All applicable statistical tests will be 2-sided and will be performed using a 5% significance level. Continuous variables will be reported as mean \pm standard deviation, or median (range or interquartile range if data are skewed) if not normally distributed; these variables will be compared using Student's t-test if normally distributed or Mann-Whitney U test if not normally distributed. Categorical variables will be expressed as total number (percentage) and will be compared by chi-squared test. For the primary endpoint, survival free from atrial arrhythmia, we will use the Kaplan-Meier survival analysis. A multivariable Cox proportional hazards model will be performed to investigate the effects of baseline characteristics in predicting ablation results, an adjustment will also be done by recruiting center. A receiver operating curve analysis will be performed to determine optimal cutoff LAWT values for predicting AF recurrence after ablation. All efforts will be done to limit missing data on outcome. Nevertheless, missing data will be reported on the final manuscript and, as much as possible, the reasons why data are missing will be documented. If missing, a simple imputation method will be applied and reported.

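### The efficiency objective is comparative, but the trial has one arm and no reference time is fixed, so the plan can only describe procedure, RF and fluoroscopy time

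*Combined protocol and SAP*

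**What the plan says.** The first secondary objective (section 2.2.2) is to determine whether the approach "permits to be more efficient in terms of procedure time, RF time, and fluoroscopy time". No comparator is named. Section 3.1 gives the design: "Single-arm, international, multicenter, prospective study". The allocation row of the timeline in section 3.8 is empty.

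Section 3.5.2.1 lists procedure time, radiofrequency time and fluoroscopy time among the acute outcomes, and the data collection sheet (Appendix 2) records them. Neither place gives a target or reference value.

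Section 3.11.2 opens with a general rule: "All applicable statistical tests will be 2-sided and will be performed using a 5% significance level". It prescribes mean with standard deviation, or median with range or interquartile range, for continuous variables, and then says "these variables will be compared using Student's t-test if normally distributed or Mann-Whitney U test if not normally distributed". Categorical variables are to be compared by chi-squared. No groups and no reference values are named.

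Section 3.11.1 assumes that the new protocol "is an acceptable alternative to the CLOSE protocol", "with the advantage of less radiofrequency applied and likely lower risk for complications". The amount of radiofrequency saved is not stated.

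**The concern.** To be more efficient is to be more efficient than something. With one arm, that something must come from outside the trial, and an outside reference is only a fair test if it is chosen before the results are known. Procedure and fluoroscopy times can be expected to differ between operators, centres and workflows, so the choice of reference series could by itself decide the conclusion. Nothing in the plan limits that choice for the time outcomes.

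What is at stake is what the trial may claim. Lower radiofrequency delivery is part of the case made for the new protocol in section 3.11.1. A report that the approach is faster, or uses less radiofrequency, would look like a planned finding when the plan contains no comparison able to produce it.

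**Working it through.** The plan states no sample size, power, effect size, standard deviation or benchmark for the time outcomes, so there is no figure to reproduce. The check is whether the documents supply either of the two things a comparative answer needs: a second group, or a reference value.

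**1. Is there a second group?** No. Section 3.1 is single-arm and the allocation row in section 3.8 is blank. Section 3.11.1 speaks of arms when it describes the confidence limit, but no second arm is defined anywhere.

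**2. Is there a reference time?** The possible sources are:
- CLOSE study (section 1): ablation-index targets, the index reached on the posterior wall, and 91.3% of patients arrhythmia-free at 12 months. No times.
- CLOSE protocol (section 3.11.1): reference for one-year clinical success. No times.
- Protocols with higher index targets (section 2.2.1): a class of comparator for long-term clinical outcome. No times.
- Single-catheter study, 50 versus 50 patients (section 1): feasibility, cost and recurrence. No times.
- Earlier single-centre series of 80 patients (section 3.13): complications only. No times.

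None gives a procedure, RF or fluoroscopy time.

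**3. Could the tests in section 3.11.2 answer the question as they stand?** Used between subgroups of the cohort (for example, first-pass isolation achieved or not), they compare patients who all had the same approach. That says nothing about whether the approach is quicker than another. Used in one-sample form, they need a reference value, which step 2 shows is absent.

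**4. Would the sample be large enough if a benchmark existed?** This is an illustration in SD units, because no SD is given. Inputs: n = 106 (section 3.11.1), and n = 95 after the stated 10% drop-out (106 × 0.9 = 95.4).
- Half-width of a 95% confidence interval for one mean = t(0.975, n − 1) / √n. For n = 106 this is 0.193 SD; for n = 95 it is 0.204 SD.
- Difference from a fixed benchmark detectable with a two-sided 5% one-sample test (normal approximation) = (1.960 + z) / √n, where z is 0.842 for 80% power and 1.282 for 90%.
- n = 106: (1.960 + 0.842) / 10.296 = 0.27 SD at 80% power; (1.960 + 1.282) / 10.296 = 0.31 SD at 90%.
- n = 95: 0.29 SD and 0.33 SD.

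So the trial could estimate the three times with useful precision and could test them against a benchmark. What is missing is the benchmark. Treating a published mean as a fixed constant also ignores its own sampling error, so the detectable differences above are optimistic.

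**The case against.** The strongest reply is that section 3.11.2 is general text, not a stated analysis of this objective. It may be meant for contrasts within the cohort, such as reasons for failed first-pass isolation or predictors of recurrence. It already provides descriptive summaries, and the times are listed and collected, so the objective does get a descriptive answer. CLOSE is also the evident reference protocol, which narrows the field. And this is one secondary objective, with no power statement or decision rule attached.

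Most of this stands, and it limits the point. Three stronger readings that a reader might draw are not supported:
- *That every named test needs two groups, so the plan contains no valid test for the times.* Mann-Whitney is a two-sample test, but Student's t-test is not specified as one- or two-sample, and both it and chi-squared have one-sample forms. The gap is the benchmark.
- *That the saving in radiofrequency is the plan's stated justification for the non-inferiority margin.* Section 3.11.1 mentions the saving when it calls the new protocol an acceptable alternative to CLOSE. The next sentence sets a 10% margin without saying that less radiofrequency justifies it. The same section also gives a limit of −0.05, which is a separate matter to resolve.
- *That the choice of comparator is wholly open.* Sections 2.2.1 and 3.11.1 point to protocols with higher index targets and to CLOSE, though for clinical outcome only.

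What the reply does not meet is the objective itself. A descriptive summary does not determine whether something is more efficient, and an implied comparator whose times, source and method of comparison are not fixed leaves the decisive choices until after the data.

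**Conclusion.** The point holds. The objective asks a comparative question, the design has no concurrent comparator, and no reference value is given for any of the three times. As written, the plan supports a description of procedure, RF and fluoroscopy time and nothing more. A statement that the approach is more efficient or uses less radiofrequency would depend on a comparator chosen after the data are seen.

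All three efficiency outcomes are affected. The size of a possible error cannot be stated, because the documents contain neither reference times nor standard deviations. The precision figures in SD units show only that 106 patients would be enough for a useful estimate.

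The conclusion rests on the text available; some pages and the figures were not. It does not assume that the tests in section 3.11.2 were intended for this objective. It does not touch the primary endpoint or the sample size. It should be corrected because it changes what the trial may claim, and the correction is cheap.

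**What to change.** Reword the first objective in section 2.2.2 as: to estimate procedure, RF and fluoroscopy time. In section 3.11.2, add that each is reported as a mean or median with a 95% confidence interval, and name the within-cohort contrasts for which the two-group tests are meant.

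If a comparison is wanted, write the reference values and their source into the plan before any data review (for example from the CLOSE report, if it gives them). Specify a one-sample test or confidence interval against those values. State the limits of a historical control: differences in centres, operators and workflow, and in how the times are measured. On the last, section 3.4.3 leaves out time spent on other substrates after isolation, so the reference must be defined in the same way. The approach is also a package (adapted index targets, single catheter, anaesthetic protocol), so a difference could not be assigned to wall-thickness adaptation alone.

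Without such a benchmark, do not report greater efficiency or less radiofrequency as a trial result.

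The cost is a change of wording, with no added patients, visits or data. The price is that the efficiency claim becomes descriptive unless a benchmark is fixed in advance.

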3. METHODS

3.1 Study design

Single-arm, international, multicenter, prospective study.

3.2 Study setting

Tertiary hospitals with an electrophysiology team of qualified investigators with proven experience in performing atrial fibrillation ablation.

3.3 Eligibility criteria

Patients will only be recruited if they fulfill the following inclusion criteria:

- Age > 18 years.
- Indication for paroxysmal atrial fibrillation ablation.
- Signed informed consent.

Patients will be excluded if they meet any of the following exclusion criteria:

- Age < 18 years.
- Pregnancy.
- Previous AF REDO procedure.
- Impossibility to perform a MDCT scan.
- Concomitant investigation treatments.
- Medical, geographical and social factors that make study participation impractical, and inability to give written informed consent. Patient's refusal to participate in the study.

3.4 Interventions

3.4.1 Pre-procedure MDCT scan

A pre-procedural multi-detector cardiac tomography (MDCT) will have to be performed in all participant subjects and centers. In the case of Teknon Medical Center, this will be done using a Revolution™ CT scanner (General Electric Healthcare). The images will be acquired during an inspiratory breath-hold using retrospective ECG-gating technique with tube current modulation set between 50% and 100 % of the cardiac cycle. CT angiographic images will be acquired during the injection of a 70 mL bolus of Iopromide 370 mg I/mL (Ultravist, Bayer Hispania, Barcelona, Spain) at a rate of 3mL/s. Other contrast agents or acquisition protocols will be permitted, according to the usual practice of the corresponding centers. Similar acquisition protocols will be adapted to the local practice and available CT scanner of each participant center. All the data will be transmitted to the core-lab (see section 3.4.2) for

post-processing and will be reconstructed into axial images with a slice thickness of 0.625 mm.

3.4.2 Image processing

MDCT images of all centers will be anonymously sent using a secure data transfer server (eCRD platform developed by the contract research organization –CRO– Xolomon SL) and analyzed by the following core-lab: ADAS 3D Medical SL headquarters (Barcelona, Spain). The ADAS 3D LA™ software (ADAS 3D Medical SL, Barcelona, Spain) will be used to obtain 3D atrial wall thickness maps. All the images obtained in the remaining participating centers will be submitted to the core-lab using a secure server. In order to obtain the atrial wall thickness a 3-step algorithm will be applied: i) the endocardial layer is defined by means of a semi-automatic segmentation based on pixel intensity thresholds; ii) the epicardial layer is defined by a manually delineation in few slices followed by an interpolation in the missing slices; iii) Finally, the wall thickness at each endocardial point is computed as the distance between each endocardial point and its projection to the epicardial shell. These three steps result in a 3D thickness map that can be introduced into CARTO® navigation system (Biosense Webster, Diamond Bar, California, US). The color map uses a color scale to depict a range of thickness red being the thinnest (< 1 mm) and purple being the thickest (> 4 mm). Yellow, green and blue will be considered the intermediate values.

The same post-processing protocol will be applied to compute the distance between each LA epicardial point and the boundaries of the esophagus, thus calculating the soft tissue thickness (i.e. separation in mm) between these two anatomic structures. The tissue thickness at each point will be color-coded in a similar way as for LAWT, and the ‘fingerprinted’ esophagus image with the tissue thickness information will be also exported into CARTO® navigation system (Biosense Webster, Diamond Bar, California, US). Figure 3 in Appendix 4 shows an example of this fingerprinted esophagus, projected onto the LA posterior wall.

3.4.3 Catheter-based radiofrequency ablation

Procedures should be performed on uninterrupted oral anticoagulation and under general anesthesia aiming to complete neuromuscular relaxation (see Appendix 3), with hemodynamic monitoring using a radial arterial line. Single venous femoral access will be mandatory. Peri-procedural anticoagulation will be performed according to local protocols but always aiming to achieve an intraprocedural activated clotting time (ACT) of 300–350 seconds.

Transeptal puncture will be preferably guided by peri-procedural transesophageal echocardiography (TOE), which does not require for an additional venous puncture. Other imaging techniques, such as intracardiac echo, will be allowed to guide the puncture for those centers without TOE availability (it will have to be collected in the data collection sheet). After the puncture, the TOE probe must be removed from the esophagus to avoid tissue overheating during RF applications. The use of a transesophageal temperature probe will be allowed at operator’s discretion. PVI will be performed point-by-point, aiming to

complete a RF circle around the PV ostia (nephroid shape) on the 3-dimensional geometry using a Thermocool SmartTouch 3.5-mm irrigated tip contact force-sensing RF ablation catheter (Biosense Webster, Inc.). In case of a common ipsilateral vein ostium, the line must be drawn around the trunk. PVI will be started in all cases at the right PVs; PV isolation initiated from the right anterior ganglionated plexi (located at the supero-anterior area of the RSPV antrum) could effectively inhibit vagal response occurrence during subsequent RF applications by increasing the basal heart rate.³⁶ RF lines will be manually traced, aiming to avoid, if possible, the 'fingerprinted' image of the esophagus, projected on the LA posterior wall (see Appendix 4). Maximal interlesion distance will be 6 mm. VisiTag settings will be as follows: catheter position stability: minimum time 3 s, maximum range 4 mm; force over time: 25%, minimum force 3 g; lesion tag size: 3 mm. The irrigation flow rate must be set to 2 ml/min during mapping and 17-30 ml/min during ablation. AI targets are defined by local AWT on the thickness color map, as follows: Thickness < 1 mm (red): 300; 1-2 mm (yellow): 350; 2-3 mm (green): 400; 3-4 mm (blue): 450; > 4 mm (purple): 500. The recommended power settings to reach these AI values will be, in general, 35W for the posterior wall and 40W for the anterior wall. Wherever local AWT is > 3 mm (green and blue colors), an increased RF power (50W) will be permitted to reach the AI target faster, particularly if the catheter is placed in an unstable place. If the targeted AI value is not reached, another lesion reaching the target must be applied.

Acute PVI will be confirmed after *first pass* with the single catheter method of demonstrating entry and exit block with the ablation catheter placed sequentially in each of the PVs or trunks. There is a minimum waiting time of 10 min after isolation of each ipsilateral PV pair; additional RF applications must be performed at reconnection sites until PVI is achieved. A carina line will have to be always performed for the right pulmonary veins, since there is anatomical³⁷ and electrophysiological evidence³⁸⁻⁴⁰ for the presence of interconnections of the ipsilateral veins in up to of $\frac{2}{3}$ of the patients referred for AF ablation.⁴¹ Additional substrate ablation to create left atrial linear lesions or any extra PV-trigger ablation like CFAE is not permitted. Atrial fibrillation that persists after PVI must be terminated with electrical cardioversion. In case other substrates have to be addressed in the same procedure (i.e. right atrial arrhythmias), the additional time, vascular accesses or catheters employed after PVI will not be taken into account for the purpose of the present study.

Of note is that complete PVI will not be considered unless a second evaluating operator confirms the absence of 'visual gaps' along the ablation lines. This second operator may be any experienced professional involved in the procedure (nurse, engineer, technician, etc.) that is able to assess the presence of gaps in a reliable manner. The visual gaps will be defined as any solution of continuity between two RF lesions tagged using the VisiTag settings previously described and a 3-mm tag size. This confirmation will have to be indicated in ALL cases in the data collection sheet. Its absence will be a reason to exclude the case from the study.

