3.10.3 CARTO® data management

CARTO® (Biosense Webster, Diamond Bar, California, US) studies of all centers will be exported and anonymously sent using a secure data transfer server (eCRD platform developed by CRO Xolomon SL) and analyzed by the following core-lab: ADAS 3D Medical SL headquarters (Barcelona, Spain). Ablation settings and RF applications will be thoroughly reviewed by an expert operator of the core-lab, to ensure compliance with the LAWT protocol. Any violation of this protocol will be considered enough reason to exclude the case from further analysis.

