1. PROCEDURE AND PATIENT DATA

FIRST OPERATOR..... Anesthetist..... EVALUATING OPERATOR.....

DATE OF THE PROCEDURE..... /..... /.....

HR ventilation Yes/No Rate Tidal vol

Age: Sex: Male //Female CHA₂DS₂-VASc = HAS-BLED:... Weight Kg Height: m

CVRF: none // HBP // Dislipemia // DM-2 // Smoker // OSA // Sport (>4 h/week x 10 y)

Underlying HD: none // Hypertensive // Ischemic // HOCM // Valvular // Other

Conduction disturbances: none // LBBB // RBBB // LAHB // LPHB // Other:

Treatment: OAC: Interrupted: Yes // NO // ¿?

TEE LA Size (mm): LVEF: Mitral annulus: cm Other:

PV anatomy: 4 indep. // Left common // Right common // Accessory veins:

LAA Closure: YES // NO Closure device type and size:

2. PROCEDURAL DATA OF PVI:

Number of femoral accesses: 1 / 2 (only 2 permitted in case of ICE use)

Ablation lines adapted to fingerprinted esophagus: YES // NO (why:))

Curve of the ablation catheter (SmartTouch®): Blue // Orange // Black

Procedure time: min FAM + Merge time: min Transeptal time: min

Transeptal puncture technique: TEE // ICE

Fluoro time: sec Fluoro dose: mGy Fluoro dose (index): Gy/cm²

RF power: anterior wall W // posterior wall W

RF time: Right PV s // Left PV s

[figure not shown]
Number of RF points: Left Right

Electrical cardioversion: Yes // No

Acute complications:

Was the procedure evaluated for the absence of gaps by the 2nd operator?: YES // NO

Select at which segment/s the subjacent rhythm was (entirely or predominantly) AF/AT: This is to assess in the future whether segments where rhythm disturbances are observed could influence catheter stability, quality of RF lesions and, ultimately, be a predictor of reconnections.

[figure not shown]
Select at which segment/s **FIRST PASS** isolation was **NOT ACHIEVED**, an explain why:

.....

.....

.....

.....

[figure not shown]
Select at which segment/s **ACUTE RECONNEXION** was observed, an explain why:

.....

.....

.....

.....

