APPENDIX 4: Representative figures

Figure 1. Aspect of the left atrial (LA) anterior wall after MDCT imaging segmentation. An analysis of the LA wall thickness (LAWT) has been performed. The color map uses a color scale to depict a range of thickness; red being the thinnest (< 1 mm) and purple being the thickest (> 4 mm). Yellow (1-2 mm), green (2-3 mm) and blue (3-4 mm) will be considered the intermediate values. The full-range color-coded LAWT map (*left image*) can be simplified using an adaptive binarization algorithm (*right image*) that helps selection the proper Ablation Index (AI) targets for each zone.

[figure not shown]

Figure 2. Aspect of the LA posterior wall after MDCT imaging segmentation. *Right image:* Full-range color-coded LAWT map as seen in CARTO. *Left image:* Binarized color-coded LAWT map integrated in CARTO.

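### The 50 W allowance in section 3.4.3 contradicts itself: its millimetre threshold means blue and purple wall, but it names green and blue

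*Combined protocol and SAP*

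**What the plan says.** Section 3.4.3 ties the AI target at each point to local wall thickness as shown on the colour map. It lists red (below 1 mm) at 300 and yellow (1-2 mm) at 350, then "2-3 mm (green): 400; 3-4 mm (blue): 450; > 4 mm (purple): 500". On power it says: "The recommended power settings to reach these AI values will be, in general, 35W for the posterior wall and 40W for the anterior wall". The exception follows directly: "Wherever local AWT is > 3 mm (green and blue colors), an increased RF power (50W) will be permitted". Its stated purpose is to get to the target sooner, above all where the catheter is unstable.

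The colour scale appears in two other places. Section 3.4.2 fixes its ends, with "red being the thinnest (< 1 mm) and purple being the thickest (> 4 mm". The Figure 1 legend in Appendix 4 gives the same ends and fills in the middle: "Yellow (1-2 mm), green (2-3 mm) and blue (3-4 mm) will be considered the intermediate values".

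Two further places bear on how the rule is checked. Section 3.10.3 states: "Ablation settings and RF applications will be thoroughly reviewed by an expert operator of the core-lab, to ensure compliance with the LAWT protocol", and makes a violation sufficient ground for dropping the case from analysis. The data collection sheet in Appendix 2 records power only as "RF power: anterior wall W // posterior wall W".

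**The concern.** The 50 W sentence defines the same region twice, once in millimetres and once in colours, and the two definitions do not match. An operator cannot follow both at a green or a purple site.

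Three things are at stake.

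- **Delivery of the intervention.** Operators work from the colour map, so the parenthesis is the half they are most likely to apply directly. Read that way, the rule allows higher power on 2-3 mm wall. It also omits wall above 4 mm, which has the highest AI target (500) and where reaching the target faster would be most useful.
- **Consistency across centres.** This is a single-arm, multicentre study of a thickness-adapted protocol. The thickness at which power may be raised should be the same at every site.
- **Compliance review.** The core-lab checks ablation settings, and a violation can remove a case from the analysis. With two possible criteria, 50 W at a green or purple site could be judged either way. Exclusion on this ground is possible but not certain.

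**Working it through.** The plan gives no statistical figure to reproduce here. The check sets the two halves of the sentence against the protocol's own scale.

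**Inputs.** Bands and AI targets come from section 3.4.3. The Appendix 4 Figure 1 legend gives the same bands, and section 3.4.2 agrees on red and purple. The default powers (35 W posterior, 40 W anterior) and the 50 W rule come from section 3.4.3.

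**Step 1: classify each band by each half of the sentence.**

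| Band | Thickness | AI target | 50 W by millimetres (> 3 mm) | 50 W by colours (green, blue) | Agree? |
|---|---|---|---|---|---|
| Red | < 1 mm | 300 | no | no | yes |
| Yellow | 1-2 mm | 350 | no | no | yes |
| Green | 2-3 mm | 400 | no | yes | **no** |
| Blue | 3-4 mm | 450 | yes | yes | yes |
| Purple | > 4 mm | 500 | yes | no | **no** |

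The millimetre half gives {blue, purple}. The colour half gives {green, blue}, that is, 2-4 mm. Blue is the only band that both include. They disagree on 2 of 5 bands.

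**Step 2: look for text that settles it.** The three statements of the scale agree with one another, so the colours are not redefined anywhere. The 50 W rule is not restated anywhere. The contradiction lies within one sentence and is not explained by missing or redacted text.

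**Step 3: size of the power difference on green wall under the colour reading.**

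- Posterior: 50 − 35 = 15 W; 50/35 − 1 = 0.429, or +43%.
- Anterior: 50 − 40 = 10 W; 50/40 − 1 = 0.25, or +25%.

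These are differences in the power setting, not in delivered dose. The AI target on green wall is 400 under either reading.

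**Step 4: could the trial data show which reading was used?** The data collection sheet cannot, because it holds one power entry per wall and none per thickness band. The exported CARTO study would be needed.

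The document does not say how often each band occurs along the ablation line, so the number of applications or patients affected cannot be estimated.

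**The case against.** The strongest reply is that this is an evident slip with little consequence. The number is the operative condition and the colours are only a gloss. The bands are printed shortly before in the same section, so a careful reader would infer blue and purple. The 35 W and 40 W settings are general recommendations, 50 W is merely allowed, and no maximum power for green wall is stated. According to the Introduction, AI already combines contact force, time and power, so at a fixed target higher power should mean a shorter application. The document gives no evidence that 50 W on 2-3 mm wall changes lesion size, safety or efficacy. Section 3.12 lists two protocol deviations (another guidance method, and ablation outside the pulmonary veins), and power is not among them. The CARTO exports are collected in any case, so the limits of the data sheet matter little.

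Most of this stands, and it limits the importance of the point. Blue and purple is the natural reading, the percentages must not be read as dose, and no harm is shown. It does not remove the contradiction. The intended meaning has to be inferred, and the half of the sentence that is probably wrong is the half written in the terms the operator sees on screen. Section 3.10.3 is broader than section 3.12: it covers ablation settings and attaches exclusion to any violation. An optional setting still needs a defined boundary if its use is audited.

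**Conclusion.** The sentence is wrong as written. Its two halves classify two of the five thickness bands differently, and the document does not resolve the conflict. The colour reading would permit 50 W on 2-3 mm wall (+15 W posterior or +10 W anterior over the general recommendation) and leave out wall above 4 mm. Red and yellow wall, the thinnest bands, are outside the allowance on both readings. AI targets, endpoints, sample size and analysis are unaffected.

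The contradiction itself rests on no assumption beyond the protocol's own scale. That blue and purple was intended is an inference from the stated threshold and from the aim of reaching the target faster. The point should be fixed, but it does not threaten the trial's conclusions.

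**What to change.** Change the parenthesis so that the allowance applies above 3 mm (blue and purple). If the investigators meant green and blue, keep the colours and change the threshold to 2-4 mm. Either way, number and colours must describe the same bands.

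Send the corrected sentence to all sites and to the core-lab, and use it in the compliance review from that date forward. Cases treated earlier should not be excluded because the operator followed the colours as printed.

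The cost is one corrected phrase and a notice. The investigators should decide whether section 5.3 calls for a formal amendment with ethics approval. Aligning the colours with the stated threshold is close to a typographical correction, whereas moving the threshold to 2-4 mm is more clearly a change of procedure.
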